## 6.2 Dose Delays

Dosing of ipilimumab or nivolumab may be held at the treating investigator’s discretion for any toxicity of any grade. Additionally, holding of the study agents may be required as indicated in the tables in **Section 6.1**.

A treatment delay of up to six weeks for nivolumab and up to 12 weeks for ipilimumab is allowable. Participants requiring a longer hold should be removed from protocol therapy. Exceptions for participants exhibiting clinical benefit may be possible with approval from the principal investigator.

If study agent dosing is held due to toxicity, the counting of cycle days and assessment schedule will continue without interruption. For example, a participant who does not receive their Cycle 3 Day 15 dose of nivolumab due to toxicity will proceed with their next regularly scheduled clinic visit (Cycle 3 Day 29) as previously planned. Alternatively, if ipilimumab is held on C3D1 and nivolumab is given, the ipilimumab dose would be omitted for that cycle. Additional interim clinic visits may be scheduled to manage toxicity, however the cycle will not restart due to dosing delays due to adverse events and the assessment schedule (including tumor imaging evaluations) will continue as originally planned.

### 6.3 Dose Reductions

There will be no dose reductions for nivolumab or ipilimumab allowed. Participants who cannot tolerate the assigned doses of nivolumab or ipilimumab should be removed from protocol therapy.

### 6.4 Overdose Management

There is no available information concerning overdose with nivolumab or ipilimumab. In case of overdose, patients must be closely monitored for signs or symptoms of adverse reactions and appropriate symptomatic treatment instituted. There are no specific antidotes. Any overdoses of either drug should be reported as an SAE to BMS. Please see section 7.3.4 for information on reporting.

## 7. ADVERSE EVENTS: LIST AND REPORTING REQUIREMENTS

Adverse event (AE) monitoring and reporting is a routine part of every clinical trial. The following list of reported and/or potential AEs (Section 7.1) and the characteristics of an observed AE (Section 7.2) will determine whether the event requires expedited reporting **in addition** to routine reporting.

### 7.1 Expected Toxicities

#### 7.1.1 Adverse Events List

In addition to the list below, please also refer to the investigator's brochure (IB) for both nivolumab and ipilimumab for comprehensive adverse event information.

##### 7.1.1.1.1. Adverse Event List for Nivolumab combined with Ipilimumab

Common adverse events associated with combination treatment include:

- Fatigue
- Fever
- Chills
- Flu-like symptoms
- Infusion-related reactions
- Headache
- Dizziness
- Hyperthyroidism or hypothyroidism
- Cough
- Dyspnea
- Pneumonitis

- Hypotension
- Dry mouth
- Anorexia
- Diarrhea
- Nausea
- Vomiting
- Dehydration
- Abdominal pain
- Colitis
- Elevated liver transaminases
- Elevated lipase and/or amylase
- Rash
- Pruritus
- Vitiligo
- Joint pain or stiffness
- Muscle soreness, weakness, stiffness, or spasms

## 7.2 Adverse Event Characteristics

- **CTCAE term (AE description) and grade:** The descriptions and grading scales found in the revised NCI Common Terminology Criteria for Adverse Events (CTCAE) version 5.0 will be utilized for AE reporting. All appropriate treatment areas should have access to a copy of the CTCAE version 5.0. A copy of the CTCAE version 5.0 can be downloaded from the CTEP web site [http://ctep.cancer.gov/protocolDevelopment/electronic\\_applications/ctc.htm](http://ctep.cancer.gov/protocolDevelopment/electronic_applications/ctc.htm).
- **For expedited reporting purposes only:**
  - AEs for the agent(s) that are listed above should be reported only if the adverse event varies in nature, intensity or frequency from the expected toxicity information which is provided.
- **Attribution** of the AE:
  - Definite – The AE *is clearly related* to the study treatment.
  - Probable – The AE *is likely related* to the study treatment.
  - Possible – The AE *may be related* to the study treatment.
  - Unlikely – The AE *is doubtfully related* to the study treatment.
  - Unrelated – The AE *is clearly NOT related* to the study treatment.

### 7.3 Expedited Adverse Event Reporting

In the event of an unanticipated problem or life-threatening complications treating investigators must immediately notify the Overall PI.

Investigators **must** report to the Overall PI any serious adverse event (SAE) that occurs after the initial dose of study treatment, during treatment, or within 100 days of the last dose of Nivolumab and 30 days of the last dose of Ipilimumab. SAEs that occur after 30 days post-treatment must only be reported to the Overall PI if they are determined to be related to Nivolumb or Ipilimumab.

For Multi-Center Trials where a DF/HCC investigator is serving as the Sponsor, each participating institution **must** abide by the reporting requirements set by the DF/HCC. This applies to any medical event equivalent to an unexpected grade 2 or 3 with a possible, probable or definite attribution, unexpected grade 4 toxicities, and grade 5 (death) regardless of study phase or attribution.

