**1.                      OBJECTIVES**

**1.1                      Study Design**

1.1.1      This is an open-label, single-arm, multicenter, phase 2 study of nivolumab 3 mg/Kg intravenously (IV) every 2 weeks (14 days) plus Ipilimumab 1 mg/Kg IV every 6 weeks (cycle length= 6 weeks) in subjects with hypermutated metastatic HER-2 negative breast cancer previously treated with 0 to 3 chemotherapy regimens in the metastatic setting. Mandatory research biopsies will be performed at baseline (if tissue is safely accessible) and at day 29 of Cycle 1 (+14 day scheduling window).

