## **4. REGISTRATION PROCEDURES**

### **4.1 General Guidelines for DF/HCC Institutions**

Institutions will register eligible participants in the Clinical Trials Management System(CTMS) OnCore. Registrations must occur prior to the initiation of protocol therapy. Any participant not registered to the protocol before protocol therapy begins will be considered ineligible and registration will be denied.

An investigator will confirm eligibility criteria and a member of the study team will complete the protocol-specific eligibility checklist.

Following registration, participants may begin protocol therapy. Issues that would cause treatment delays should be discussed with the Overall Principal Investigator (PI). If a participant does not receive protocol therapy following registration, the participant's registration on the study must be canceled. Registration cancellations must be made in OnCore as soon as possible.

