## Summary of Specimens

Research Sampling	Timepoint	Contents	Destination
Archival Tissue	Anytime on study	1 FFPE Block or 10-20 5 micron unstained slides	Current DFCI CRC
Fresh Tissue	Baseline* (within 28 days of C1D1, prior to treatment start)	5-7 cores	RNAlater Cores – Breast Bank
	C1D29 (+14 day scheduling window)	5-7 cores	Formalin Cores – Breast Bank
	End of Treatment (Optional)	5-7 cores	External Sites Only: OCT Core – Breast Bank
Blood	Baseline*, Restaging Visits, Time of Progression	1 – 10mL Streck Tube (cfDNA)	Breast Bank
		5 – 10mL CPT tubes (PBMCs)*	Mayer 308 / [name]
Stool	Baseline*	Home Collection Kit (DNA Genotek)	Breast Tumor Immunology Lab/ [name], PhD
	At C1D29 (any time between C1D29 and C2D1)		
	End of treatment		
	Optional collection at the time of grade $\geq 2$ diarrhea		

Note: The “Breast Bank” and Core Blood and Tissue Bank are the same lab and interchangeable

\*Baseline samples preferably completed after registration or on Cycle 1 Day 1 prior to treatment start (once a study ID is assigned). Baseline samples completed during screening will not be a violation.

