#### Safety and tolerability

All patients will be evaluable for toxicity from the time of their first treatment with any study agent. Toxicity will be graded according to NCI CTCAE, Version 5.0. Toxicities will be summarized by maximum grade and by treatment arm. Incidence rate of each toxicity will be reported with 95% exact CI. The incidence rates of any grade 3+ toxicity will be compared between two arms using Fisher's exact test.

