#### 13.6.2 Evaluation of Safety

The safety population will be used in the safety data summaries. The safety population consists of all patients who took at least one dose of any randomized treatment and who have at least one post-baseline safety assessment. Note that a patient who had no adverse events constitutes a safety assessment. Patients who have received at least one dose of study drug but have no post-treatment safety data of any kind would be excluded.

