### **Risks of Research Biopsy and Procedures for Minimizing Risk**

#### **Potential risks according to site are:**

*Skin/chest wall (punch biopsy):*

- Likely: local discomfort and minor bleeding
- Less likely: moderate or major bleeding, or infection

*Lymph node, liver, or bone (core needle biopsy):*

- Likely: local discomfort and minor bleeding
- Less likely: moderate or major bleeding, need for blood transfusion, hospitalization due

to bleeding or other complications, infection, damage to adjacent organs. Additional risks may be present if intravenous conscious sedation is required

*Breast (core biopsy):*

- Likely: local discomfort and minor bleeding.

- Less likely: moderate or major bleeding, need for blood transfusion, hospitalization due

to bleeding or other complications, infection, pneumothorax, damage to adjacent organs.

*Pleural fluid (thoracentesis):*

- Likely: local discomfort and minor bleeding
- Less likely: moderate or major bleeding, need for blood transfusion, hospitalization due to bleeding or other complications, infection, pneumothorax, damage to adjacent organs

*Ascites fluid (paracentesis):*

- Likely: local discomfort and minor bleeding
- Less likely: moderate or major bleeding, need for blood transfusion, hospitalization due to bleeding or other complications, infection, bowel perforation or damage to adjacent organs. In order to minimize the risk of a biopsy, only qualified personnel will perform these procedures.

Prior to the procedure, the physician performing the procedure will discuss the risks with each study participant, answer any questions, and obtain separate procedure consent. Patients will be evaluated for comorbidities or concomitant medications that may increase the risk of potential complications. For biopsies of lesions that are not superficial and clearly palpable, imaging studies such as CT or ultrasound will be used to guide the biopsy in order to minimize the risk of damage to adjacent structures. After lymph node biopsies, patients will be observed a minimum of 2 hours (range 2-4 hours) after the procedure, or according to standard institutional guidelines. After liver biopsies, patients will be observed a minimum of 4 hours (range 4-6 hours) after the procedure, or according to standard institutional guidelines. Less than the goal quantity of tissue is accepted for each type of biopsy, and will be left to the clinical judgment of the physician performing the procedure.

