### 3.7.2 Initiation of Therapy

Participants must be registered with the DF/HCC CTMS before the initiation of treatment or other protocol-specific interventions. Treatment and other protocol-specific interventions may not be initiated until the Participating Institution receives confirmation of the participant's registration from the Coordinating Center. The DF/HCC Sponsor and DFCI IRB must be notified of any violations to this policy.

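### SAE reporting to the Overall PI and the safety analysis start at first dose, so a foreseen, non-life-threatening serious complication of the pre-dose research biopsy has no clear route to the Overall PI or DSMC

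*Combined protocol and SAP*

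**What the plan says.** **The procedure.** Section 1.1: "Mandatory research biopsies will be performed at baseline (if tissue is safely accessible"), with a second biopsy at C1D29. Section 9 asks for 5-7 cores at baseline, within 28 days before C1D1. For lymph node, liver or bone cores, Appendix B puts "moderate or major bleeding, need for blood transfusion, hospitalization due" to bleeding among the less likely risks. Hospitalization meets the seriousness criteria in Section 7.3.4.

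**Rules that start at dosing.**
- Section 7.3 has investigators report to the Overall PI "any serious adverse event (SAE) that occurs after the initial dose of study treatment".
- Section 13.4: "All patients will be evaluable for toxicity from the time of their first treatment with any study agent".
- Section 13.6.2: "The safety population consists of all patients who took at least one dose of any randomized treatment" and have a post-baseline safety assessment.
- Section 7.2 grades attribution, from definite to unrelated, against study treatment only. There is no category for a research procedure.

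**Patients never dosed.** Sections 13.1 and 13.6.1 call them unevaluable and replace them. At DF/HCC institutions (4.1), "If a participant does not receive protocol therapy following registration", the registration has to be cancelled. At other sites (4.3) the subject is instead recorded as off-study, with date and reason.

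**Biopsy and registration.** The footnote to the Summary of Specimens in Section 9 prefers sampling after registration but adds: "Baseline samples completed during screening will not be a violation". Appendix E, 3.7.2, which governs external sites, says: "Treatment and other protocol-specific interventions may not be initiated until the Participating Institution receives confirmation" of registration. Appendix E, 2.3, likewise puts registration ahead of research activities.

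**The concern.** The baseline biopsy is an invasive procedure done for research, before the participant can have had any benefit from treatment. If the reporting clock starts afterwards, serious complications of the kind Appendix B foresees can bypass the people who could act on a cluster of them. The harms most likely to drop out are those bad enough to prevent treatment. Such a patient leaves the safety population and is replaced by someone who did start. A safety report built only on dosed patients would then understate the procedural risk of taking part.

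**Working it through.** No figure in the plan is in dispute, so the check is mainly a reading of the routes side by side. The test case is a pre-dose bleed after a liver core, Grade 2 or 3, leading to hospitalization, not life-threatening, and of a kind listed in Appendix B.

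| Route | Does the test case reach the Overall PI or DSMC? |
|---|---|
| SAE window, 7.3 | No. The event precedes the first dose. |
| Immediate notice of unanticipated or life-threatening problems, 7.3 | Not clearly. The complication is foreseen and not life-threatening. |
| Multicenter rule, 7.3 | No. Grade 2-3 counts only if unexpected and at least possibly attributed. Under 7.2 a pre-dose event can only be unrelated to study treatment. |
| Table in 7.3.1 | Not required for unrelated Grade 2-3, expected or not. |
| IRB reporting, 7.3.1 | DF/HCC sites send all SAEs to the IRB office. Other sites follow local IRB policy and forward the form on the table's timelines. Neither is a stated route to the DSMC. |
| Reporting to the drug supplier, 7.3.4 | Framed around use of the supplier's product; no pre-dose start is stated. |
| Routine forms, 7.4 | Grade 2+ events go to the Overall PI in routine data, with no stated start. The calendar's first adverse event evaluation is at C1D1, done before dosing. A dosed patient may be picked up here; a never-dosed patient has no evaluation at screening. |
| DSMC information, 12.2 | May include unexpected Grade 2+ events that have been reported, so it depends on the routes above and on how the event is classed. |

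Unexpected Grade 4 and fatal events do have routes in 7.3 and 7.3.1 with no first-dose limit.

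**Effect on the safety table (illustration).** Suppose one patient is harmed by the baseline biopsy, is never dosed and is replaced, all patients are biopsied, and no dosed patient has such an event.
- Planned table: 0/30. Exact 95% upper limit = 1 - 0.025^(1/30) = 11.6%.
- All biopsied patients: 1/31 = 3.2%, exact 95% CI 0.1% to 16.7%.

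**Chance that at least one event occurs (illustration).** The documents give no biopsy complication rate, so take an assumed risk q of 1% to 5% per biopsy. For the number of biopsies n, the power table in 13.4 works with 15 or 20 pairs, and 30 is the full treated sample. The formula is 1 - (1 - q)^n.
- n = 15: 1 - 0.99^15 = 0.140; 1 - 0.95^15 = 0.537.
- n = 20: 1 - 0.99^20 = 0.182; 1 - 0.95^20 = 0.642.
- n = 30: 1 - 0.99^30 = 0.260; 1 - 0.95^30 = 0.785.

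These are chances that an event happens. They are not chances that it goes unreported.

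**The case against.** The strongest reply is that Section 7.3 should not be read through one sentence. Its opening and its multicenter paragraph carry no first-dose limit, nor do the all-SAE rule for DF/HCC sites in 7.3.1 or the Grade 2+ rule in 7.4. The fatal-event footnote in 7.3.1 turns on being enrolled and actively participating. Biopsy bleeding is absent from the expected list in 7.1, so it might be classed as unexpected and reach the DSMC. The C1D1 evaluation precedes dosing, so every dosed patient has an assessment after the biopsy. A dosed safety population also suits an objective about the safety of the combination.

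Much of this stands, and it rules out several stronger readings that a reader might infer:
- That biopsy harm is never captured. The routes just listed contradict it.
- That half of all mandated biopsies, 30 of 60, fall outside collection. Dosed patients are assessed before dosing at C1D1, the biopsy depends on access, and Appendix B does not mandate lung cores.
- That any injured, untreated patient vanishes from the record. Cancellation is the rule in 4.1 only; 4.3 keeps a record. Nothing in 4.1 says that cancellation erases an event already reported.
- That the registration conflict is trial-wide. Appendix E is written for sites outside DF/HCC.

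The reply does not settle the test case. Even if classed as unexpected, an unrelated Grade 2-3 event is not required in the 7.3.1 table. IRB reporting is not review by the Overall PI or DSMC. The dosed safety population is defensible for drug toxicity, but nothing else in the plan reports procedural harm in those never dosed.

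**Conclusion.** The point holds in a limited form. A serious, foreseen, non-life-threatening complication of the baseline biopsy has no clear route to the Overall PI or DSMC. In a patient who is then dosed, it may still be found at the C1D1 evaluation and on routine forms, although 13.4 starts toxicity evaluability at first treatment. In a patient never dosed, it is absent from the safety analysis and the patient is replaced; at DF/HCC institutions the registration is also cancelled.

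The size cannot be estimated from the documents. Under the assumed 1% to 5% risk, at least one such event occurs with probability 14% to 64% for 15 to 20 biopsies and 26% to 79% for 30. The number of pairs is a lower bound on baseline biopsies, and 30 assumes every treated patient has accessible tumor. The reading of the routes does not depend on these figures. It rests on the protocol text alone, since the IRB policy that 7.3.1 refers to is not part of it.

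**What to change.** - **7.3 and 12.2:** start reporting of SAEs attributable to protocol-mandated procedures to the Overall PI at the first such procedure, and include them in the DSMC information. Drug-related reporting can stay as it is.
- **7.2:** add attribution to research procedures alongside attribution to study treatment.
- **4.1:** keep participants who were biopsied but never dosed on record as off-study with a reason, as 4.3 already does.
- **13.4 and 13.6.2:** list biopsy complications over all biopsied patients, separately from the drug safety tables.
- **Section 9 and Appendix E (2.3, 3.7.2):** for external sites, reconcile whether a baseline sample may be taken before registration is confirmed.

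The cost is amendment wording and a small amount of extra data entry for a few pre-dose events. No efficacy analysis or evaluable-patient count changes.

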#### 7.3.1 Reporting to the Institutional Review Board (IRB)

Investigative sites within DF/HCC will report all serious adverse events directly to the DFCI Office for Human Research Studies (OHRS) per the DFCI IRB reporting policy.

Other investigative sites will report to their respective IRBs according to the local IRB’s policies and procedures in reporting adverse events. A copy of the submitted institutional AE form should be forwarded to the Overall PI within the timeframes detailed in the table below.

Attribution	DF/HCC Reportable AEs				
	Gr. 2 & 3 AE Expected	Gr. 2 & 3 AE Unexpected	Gr. 4 AE Expected	Gr. 4 AE Unexpected	Gr. 5 AE Expected or Unexpected
Unrelated Unlikely	Not required	Not required	5 calendar days #	5 calendar days	24 hours*
Possible Probable Definite	Not required	5 calendar days	5 calendar days #	5 calendar days	24 hours*
# If listed in protocol as expected and not requiring expedited reporting, event does not need to be reported.					
* For participants enrolled and actively participating in the study or for AEs occurring within 30 days of the last intervention (100 days from last dose of nivolumab), the AE should be reported within 1 business day of learning of the event.					

The Overall PI will submit AE reports from outside institutions to the DFCI OHRS according to DFCI IRB policies and procedures for reporting adverse events.

### 7.3.2 Expedited Reporting to the Food and Drug Administration (FDA)

The Overall PI, as study sponsor, will be responsible for all communications with the FDA. The Overall PI will report to the FDA, regardless of the site of occurrence, any serious adverse event that meets the FDA's criteria for expedited reporting following the reporting requirements and timelines set by the FDA.

Any report that meets FDA reporting requirements should also be submitted to BMS per section 7.3.4. These events are generally those that are both serious, at least possibly related to the investigational product(s), and are unexpected.

### 7.3.3 Expedited Reporting to Hospital Risk Management

Participating investigators will report to their local Risk Management office any participant safety reports or sentinel events that require reporting according to institutional policy.

### 7.3.4 Expedited Reporting to BMS

SAEs, whether related or not related to study drug, and pregnancies must be reported to BMS within 24 business hours of the awareness of the event. SAEs must be recorded on a Medwatch Form 3500A.

**SAE Email Address:** [contact]

**SAE [contact]

Adverse events generally considered serious are those that occur at any dose during any use of BMS product that:

- Results in death
- Is life-threatening (defined as an event in which the participant was at risk of death at the time of the event; it does not refer to an event which hypothetically might have caused death if it were more severe)
- Requires inpatient hospitalization or causes prolongation of existing hospitalization
- Results in persistent or significant disability/incapacity
- Is a congenital anomaly/birth defect
- Is an important medical event (defined as a medical event(s) that may not be immediately life-threatening or result in death or hospitalization but, based upon appropriate medical and scientific judgment, may jeopardize the subject or may require intervention [eg, medical, surgical] to prevent one of the other serious outcomes listed in the definition above.) Examples of such events include, but are not limited to, intensive treatment in an emergency room or at home for allergic bronchospasm; blood dyscrasias or convulsions that do not result in hospitalization.)
- Suspected transmission of an infectious agent (eg, pathogenic or nonpathogenic) via the study drug is an SAE.

A planned medical or surgical procedure is not, in itself, an SAE. Generally, any events that meet any of the seriousness criteria listed above and that are caused by progression of the disease under the study (metastatic breast cancer) are not reportable. Any instance of pregnancy, overdose, potential drug-induced liver injury (DILI), and secondary malignancies, though not necessarily considered serious per these definitions should be reported as SAEs.

If only limited information is initially available, a follow-up report is required and should include the same investigator term(s) initially reported.

If an ongoing SAE changes in its intensity or relationship to study drug or if new information becomes available, a follow-up SAE report should be sent within 24 hours of awareness to BMS (or designee) using the same procedure used for transmitting the initial SAE report.

All SAEs should be followed to resolution or stabilization.

